## 23.4 Inclusion in analysis

The principal analysis will be performed on the ITT population as defined above, analysing participants with available outcome data in their randomised groups.

## 23.5 Subgroup analysis

Pre-specified subgroup analyses will be finalised in the SAP. These will include exploring the possible treatment effect modification of age group (<50 years or ≥50 years) as a clinically important factor. Analyses will use treatment by factor interactions. Results from these analyses will be viewed as exploratory and interpreted with caution.

#### 23.6 Interim analyses

The main outcomes will be analysed as stated in the analysis plan once the trial follow-up has been completed. No formal interim analyses of treatment effect are planned for any of the trial outcomes and will be performed only where requested by the DSMC.

## 23.7 Stopping rules

As no formal interim analyses are planned, no stopping rules have been incorporated into the trial design. An independent DSMC will review the accumulating data at regular intervals and may recommend pausing or stopping the trial in the event of safety concerns.

## 23.8 Level of Statistical Significance

Non-inferiority comparisons will use one-sided 2.5% significance which is equivalent to the lower bound of the 95% confidence interval being compared to the non-inferiority margin. If the Self-directed rehabilitation is found to be non-inferior to physiotherapist-supervised rehabilitation then superiority will also be tested at 2.5% (1-sided) significance. The remaining superiority comparisons and secondary outcome analyses will use a two-sided 5% significance and 95% confidence intervals throughout.

## 23.9 Procedure for accounting for missing data

The trial will attempt to collect data as completely as possible. Any missing data will be summarised by treatment group and patterns analysed. Unavailable observations due to missed questionnaires or to a participant leaving the trial prematurely are assumed to be similar to observed outcomes from similar participants at the same time points (i.e. missing at random (MAR)). The multilevel mixed effects regression model including all participants with outcome data at other timepoints, and adjusted for minimisation factors or important prognostic factors is expected to produce unbiased results under a MAR mechanism (34) and therefore we do not anticipate using multiple imputation for missing outcome data in the analysis. The potential impact of informative missing data (missing not at random) on the treatment effect in the OSS at 6 months will be investigated using Stata's 'rctmiss' command or similar approaches if there is sufficient or differential missing data.

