#### 23.3 Description of Statistical Methods

Standard descriptive statistics will be used to summarise the baseline participant demographic characteristics by treatment group using means with standard deviation or medians with interquartile ranges as appropriate for continuous variables and numbers with percentages for binary or categorical variables. It is anticipated that all statistical analyses will be undertaken using Stata (StataCorp LP, www.stata.com) or other well-validated statistical software.

A non-inferiority trial aims to demonstrate that a new treatment is not clinically worse than the active control by more than a predefined amount and therefore the interest is one-sided. The new treatment may be better than the control, but it must not be inferior. We therefore define a maximum difference between the two groups in a given direction we are prepared to tolerate and

still consider the new treatment clinically not inferior to the standard treatment. This difference is the non-inferiority margin ( $\Delta_M$ ). We then test the null hypothesis that a difference greater than  $\Delta_M$  exists in favour of the control ( $H_0$ :  $\Delta \geq \Delta_M$ ). This is assessed by constructing a 95% confidence interval for the difference between the two treatments ( $\Delta$ ) which should be above the non-inferiority margin for the new treatment to be declared non-inferior and reject the null hypothesis in favour of the alternative ( $H_A$ :  $\Delta > -\Delta_M$ ). To estimate  $\Delta$ , the primary outcome measure, OSS at 6 months will be compared between treatment groups as the dependent variable in a mixed effects linear regression model adjusting for the minimisation factors (age and centre). A fixed effect will be used to account for age and a random effect will be included to account for any heterogeneity due to recruitment centre.

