The primary analysis will be performed using a treatment policy, in which all randomised participants with available data are analysed according to their treatment allocation regardless of whether intercurrent events occur (30, 31). Given the nature of the interventions as described in Section 13, any trial-specific intercurrent events which are likely to occur in the trial setting and not in routine clinical practice are expected to be non-significant. For example, it is possible for participants in both self-directed rehabilitation and usual care groups to access further physiotherapy treatment. To assess the impact of such intercurrent events or similar on the non-inferiority conclusion, we will consider defining additional secondary estimands. Details of the estimands and estimator strategy will be defined in the SAP and finalised following a blinded review of the data before the primary outcome analysis data lock (32).

Additional analyses including data from all timepoints in a multilevel linear regression model will be used to explore the recovery trajectory between the two groups for the OSS score using the area under the curve (AUC) based on a summary statistics approach (33). Similar mixed effects linear regression models will be used to analyse continuous secondary outcomes (PROMIS, EQ5D- 5L, SEE Scale) over time. The number and proportion of participants experiencing complications will be summarised by treatment group and compared using an adjusted logistic regression model if sufficient complications occur.

Results will be reported in line with the CONSORT statement and any appropriate extensions and will be described fully in a separate SAP. A single final unblinded statistical analysis will take place after all follow-up has been completed, and sufficient time has been allowed for data collection and cleaning.

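### Section 23.9 claims missing-at-random protection from an all-timepoints model, but the primary non-inferiority model in section 23.3 uses only the 6-month OSS

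*Protocol*

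**What the plan says.** Section 23.3 sets out how the non-inferiority difference is estimated: "OSS at 6 months will be compared between treatment groups as the dependent variable in a mixed effects linear regression model", adjusted for the minimisation factors. On the model's structure it says "A fixed effect will be used to account for age and a random effect will be included to account for any heterogeneity due to recruitment", the last term meaning the recruiting hospital. It names no participant-level effect and no 2- or 4-month OSS.

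The analysis set is described twice. Section 23.3 says that "all randomised participants with available data are analysed according to their treatment allocation", and section 23.4 restates this as "analysing participants with available outcome data in their randomised groups". Neither says whether the available data must be the 6-month score.

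The model that uses every visit appears later in section 23.3, in a different role: "Additional analyses including data from all timepoints in a multilevel linear regression model will be used to explore the recovery trajectory", summarised by area under the curve.

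Section 23.9 assumes MAR. It takes the view that "The multilevel mixed effects regression model including all participants with outcome data at other timepoints, and adjusted for minimisation factors" can be relied on for unbiased estimates, and "therefore we do not anticipate using multiple imputation for missing outcome data in the analysis". A missing-not-at-random analysis of the 6-month OSS is planned using Stata's '"rctmiss' command or similar approaches if there is sufficient or differential missing data".

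**The concern.** The reason given for not imputing is a property of a model that borrows from a participant's other visits. A model with one outcome row per participant, at 6 months, and a random effect for centre only does not have that property. A participant without a 6-month OSS contributes nothing to its likelihood, whatever was returned at 2 and 4 months.

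Section 23.2 allows for 20% loss, so this could affect about 243 of 1214 participants. The trial is open-label, and only the usual care group is contacted about physiotherapy attendance roughly every 3 weeks (section 10). Missingness that differs by arm is therefore plausible, although the documents do not establish its direction. What is at stake is the single comparison that decides the trial, against a margin of 2.5 points.

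**Working it through.** **1. The plan's own figures.** Section 23.2 gives SD 12, margin 2.5, one-sided 2.5% significance, 90% power and 20% loss.

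- Per arm: n = 2 × 12² × (1.960 + 1.282)² / 2.5² = 484.2, so 485, and 970 in total.
- 970 / 0.8 = 1212.5, so 1213, or 1214 for equal arms.
- 20% of 1214 = 242.8, about 243 participants without a 6-month OSS.

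The stated sample size reproduces and is not in question.

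**2. The two model descriptions side by side.**

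| | Primary model, 23.3 | Model relied on in 23.9 |
|---|---|---|
| Outcome | 6-month OSS | OSS at several visits |
| Random effect named | Centre | Multilevel, not specified |
| Has 2- and 4-month OSS but not 6-month | No contribution | Included |
| Role | Non-inferiority test | Matches the additional trajectory analysis in 23.3 |

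**3. When the 6-month-only difference is biased.** Let z be the standardised 4-month OSS, ρ its correlation with the 6-month OSS, and let the log-odds of a missing 6-month score be linear in z. In one arm, the mean of the observed 6-month scores is shifted by

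shift = 12 × ρ × E[z | 6-month OSS observed].

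The bias in the treatment difference is the self-directed shift minus the usual care shift. It cancels when both the missing rate and the dependence on z are equal across arms, and does not cancel if either differs.

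**4. Size, under assumed inputs.** These are not in the documents: ρ = 0.75, the missingness odds ratios (OR) per SD of 4-month OSS, and the split of missingness between arms. From the documents: SD 12, 607 per arm, margin 2.5. The true difference is set at -2.5, so the correct rate of declaring non-inferiority is 2.5%. With about 485 observed per arm, SE = 12 × √(2/485.6) = 0.77, falling slightly to about 0.76 under selective missingness.

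False non-inferiority = Φ(bias/SE − 1.96).

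| Missing, usual care / self-directed | OR, usual care / self-directed | Shifts (points) | Bias | False non-inferiority |
|---|---|---|---|---|
| 20% / 20% | 1 / 1 | 0 / 0 | 0 | 2.5% |
| 20% / 20% | 0.5 / 0.5 | 1.16 / 1.16 | 0 | 2.5% |
| 20% / 20% | 0.7 / 0.6 | 0.63 / 0.88 | +0.25 | 5.2% |
| 15% / 25% | 0.5 / 0.5 | 0.88 / 1.44 | +0.56 | 11% |
| 20% / 20% | 1 / 0.5 | 0 / 1.16 | +1.16 | 33% |
| 20% / 20% | 0.5 / 1 | 1.16 / 0 | −1.16 | below 0.1% |

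Example, fifth row: 12 × 0.75 × 0.129 = 1.16, and Φ(1.16/0.763 − 1.96) = Φ(−0.44) = 0.33. Simulation of 4,000 trials per scenario agrees (third row +0.27 and 5.4%; fifth row +1.15 and 32%). At ρ = 0.5 the fifth scenario falls to +0.77 and 17%.

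**5. What using the earlier OSS recovers.** In the same simulations, a likelihood estimate using the 4-month OSS had bias within 0.02 points and error of 2.2% to 2.6% in every scenario, provided everyone supplied the 4-month score. If half of those missing at 6 months also lack it, about +0.5 points of bias remain in the fifth scenario (error about 10%). If three quarters lack it, about +0.8 remain (about 19%).

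**The case against.** The strongest defence is that section 23.9 describes the intended primary model and section 23.3 is shorthand. The phrase about available outcome data in 23.4 does not specify 6 months, and 23.9 goes straight on to the 6-month treatment effect. This reading is possible, so a reader should not conclude that a complete-case primary analysis is certain. But it conflicts with the model as 23.3 states it and with the placing of the all-timepoints model under additional analyses, so the sections must be reconciled either way.

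Section 23.3 also defers details of estimands and estimators to the SAP. That leaves room to settle the matter before data lock. It does not remove the conflict, because the protocol has already fixed the outcome, covariates, random effect and missing-data rationale.

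Four stronger readings are tempting and are not supported:

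- That the 6-month-only difference is valid only if missingness is unrelated to earlier OSS. Equal rates and equal dependence in both arms give about no bias.
- That the error runs towards a false claim of non-inferiority. Nothing in the documents shows which arm would lose its poor recoverers, and the mirror pattern biases the other way.
- That multiple imputation is ruled out. Section 23.9 says only that it is not anticipated.
- That nothing guards against the problem. Missingness will be summarised by arm, its patterns examined, and a missing-not-at-random analysis run if missingness is sufficient or differential. These are useful, but the last is a sensitivity analysis with no stated trigger and does not change the primary estimate.

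**Conclusion.** The inconsistency stands on the text alone: the MAR property that section 23.9 uses to set multiple imputation aside belongs to a model that section 23.3 does not use for the primary test. As written, earlier OSS from participants missing at 6 months is left out of the non-inferiority comparison.

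The size is conditional. In the scenarios with positive bias it ranges from about +0.25 to +1.15 points, 10% to 46% of the margin (0.25/2.5 and 1.15/2.5), with false non-inferiority of about 5% to about 33%. It is nil when the arms behave alike and about −1.1 to −1.2 when the pattern is reversed. These figures rest on assumed correlations and dropout mechanisms and are illustrative. The largest needs strong dependence in one arm and none in the other. Using the earlier OSS helps only for participants who supplied it. The sample size is unaffected.

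**What to change.** Choose one of two routes and make sections 23.3, 23.4 and 23.9 agree.

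- **Preferred, because 23.9 already invokes it:** in 23.3, take the 6-month treatment contrast and its 95% confidence interval from a repeated-measures model of OSS at 2, 4 and 6 months, with treatment-by-time terms, age, a centre random effect and within-participant correlation. State in 23.4 that participants with at least one follow-up OSS are included. Keep the 6-month-only model as a sensitivity analysis.
- **Alternative:** keep the 6-month-only primary model and add multiple imputation by arm using the 2- and 4-month OSS, replacing the sentence in 23.9 that does not anticipate it.

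The exact covariance structure can be left to the SAP. Stating what counts as sufficient or differential missing data would help, but is not needed to remove the contradiction.

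The cost is wording in the protocol and SAP before data lock. The 2- and 4-month OSS are already scheduled, and no extra participants or data are needed.

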# **23.10** Procedures for reporting any deviation(s) from the original statistical analysis plan Any deviation(s) from the original SAP will be described in the final statistical report.

#### 23.11 Internal pilot/Decision Points

An internal pilot is planned that will progress seamlessly to the definitive trial if predefined progression criteria are reached. Data from the internal pilot trial will contribute to the final analysis. The purpose of the internal pilot is to ensure that the projected site enrolment rate and recruitment rate can be achieved.

Stop-go criteria for the pilot phase are given in Table 8 together with the definitions of how each will be measured. The criteria will be reviewed after 9 months of recruitment.

Table 8: Stop-go	criteria	for internal	nilat nhase
Tuble 6. Stup-yu	criteriu	ioi iiileiiiai	piiot piiuse.

No. of participants recruited	No. sites opened	Recruitment rate/site/month	Progression guidance
≥200	9	3	Continue with trial – no action required
100-199	5-8	1.5-2.9	Continue with trial – action required:  • Review recruitment strategies, consider modification and monitor closely
≤99	≤4	≤1.4	Review with funder

The Trial Management Group (TMG) will closely monitor the progression criteria during the internal pilot, and together with the Trial Steering Committee (TSC) and DSMC will perform a full review towards the end of the internal pilot. Guided by the TSC, the funder will make the final decision to terminate the trial.

The internal pilot trial will mirror the procedures and logistics undertaken in the main definitive trial. It is intended that the study will progress seamlessly into the main phase, with internal pilot participants included in the final analysis. Should a decision be made to stop the trial any data collected would be presented, and together with the funder it would be decided upon whether participants would be followed up as per protocol.

#### 24 HEALTH ECONOMIC EVALUATION

A prospective economic evaluation, conducted from NICE's recommended NHS and personal social services perspective (20) is integrated into the trial. A health economics analysis plan will be drafted early in the trial and finalised prior to the final analysis data lock. Primary research methods will be followed to estimate the costs of the management methods, including the costs of physiotherapists and other health professionals, physiotherapy sessions in outpatient departments, support materials and associated administrative activities. Broader resource utilisation will be captured through patient questionnaires completed at baseline and at 2, 4 and 6 months post randomisation. Unit costs for resource inputs identified will largely be derived from national reference tariffs, although primary research that uses established accounting methods may also be required. EQ-5D-5L responses will be used to generate quality adjusted life-years (QALYs) based upon baseline-adjusted utility curves using the trapezoid rule. Utility weights for EQ-5D-5L health states will be estimated using an interim crosswalk algorithm (35) until a national tariff set for the EQ-5D-5L is formally recommended by NICE. Regression methods, accounting for clustering effect, with multiple imputation of missing data if evidence supports missing at random assumption as the base-case missingness mechanism, will be conducted for costs and QALYs to generate within-trial estimates of incremental cost-effectiveness associated with the self-directed rehabilitation programme. Sensitivity analyses will be undertaken to assess the impact of areas of uncertainty surrounding components of the economic evaluation.

The sensitivity analyses will include re-estimation of cost-effectiveness under alternative missing data mechanisms, and re-estimation of cost-effectiveness assuming a broader societal perspective. The latter will incorporate direct costs to trial participants, economic values for informal care provided by family and friends and economic values associated with productivity losses; the values of these broader resource consequences will be informed by responses to questions in the patient completed questionnaires.

If incremental costs and benefits are not convergent over the trial follow-up period of the main randomised controlled trial, decision-analytic modelling will be used to extrapolate the impact of the self-directed rehabilitation programme beyond the follow-up period. Accepted guidelines for good practice in decision-analytic modelling will be followed (36). A de novo model structure will capture progression using health states that represent the important natural history and clinical- and event-related activity following proximal humerus fracture and its management methods, the appropriate model type (e.g., Markov or discrete-event simulation approach) and the appropriate analytical framework (e.g., cohort analysis versus individual-level simulation). Parameter inputs will be informed by data from the main randomised controlled trial supplemented by data from targeted

literature searches. Multi-parameter uncertainty in the model will be addressed using probabilistic sensitivity analysis.

Cost-effectiveness acceptability curves will be used to show the probability of cost-effectiveness of the self-directed rehabilitation programme at alternative cost-effectiveness thresholds held by decision-makers.

## **25 DATA MANAGEMENT**

The data management aspects of the trial are summarised here with details fully described in the trial-specific Data Management Plan. See section 29, "Participant confidentiality" for information on management of personal data.

#### 25.1 Source Data

Source documents are where data are first recorded, and from which participants' CRF data are obtained. Source data is outlined in section 9.

#### 25.2 Location of source data

The location of source data in the trial is listed in the tables within section 9.

## 25.3 CRFs

The Investigator and trial site staff will ensure that data collected on each participant is recorded in the CRF as accurately and completely as possible. All appropriate Investigator observations will be transcribed into the CRFs from the relevant source data held in the site medical record(s).

All documents will be stored safely in confidential conditions. On all trial-specific documents, other than the signed ICF, the participant will be referred to by the trial participant number, not by name.

## 25.4 Source data to be recorded directly on the CRFs

CRF entries will be considered source data if the CRF is the site of the original recording (e.g. there is no prior written or electronic record of data).

#### 25.5 Non-CRF data

All trial data will be recorded on the CRFs. No additional data will be held outside of the CRFs.

#### 25.6 Access to Data

To ensure compliance with regulations, direct access will be granted to authorised representatives from the Sponsor and host institution to permit trial-related monitoring, audits and inspections. The data submitted by trial participants directly via the trial database (i.e. electronic participant reported outcomes) will also be made available to the participating site that recruited the participant; this is detailed within the PIS so that participants are aware of who will have access to this data.

Members of the trial team will only be able to access data that they need to, based on their roles and responsibilities within the trial.

#### 25.7 Data Recording and Record Keeping

The CRFs will be designed by members of the trial management team which will include the CI, trial statistician(s) and trial manager.

Data will, wherever possible, be collected in electronic format with direct entry onto the trial database by site staff or participants. Electronic data collection has the major advantage of building "data logic" into forms, minimising missing data, data input errors and ensuring the completeness of consent and assent forms. REDCap is a secure, web-based application designed to support data capture for research studies, providing 1) an intuitive interface for validated data entry; 2) audit

trails for tracking data manipulation and export procedures; 3) automated export procedures for seamless data downloads to common statistical packages; and 4) procedures for importing data from external sources.

All data entered will be encrypted in transit between the client and server. All electronic patient-identifiable information, including electronic ICFs, will be held on a server located in an access-controlled server room at the University of Oxford.

The database and server are backed up to a secure location on a regular basis. Details of the data collected, where it is stored and who has access to it along with a fair processing statement will be available for the participants within the trial PIS.

Personal identifiable data will be kept separately from the outcome data obtained from or about the patients. Participants will be identified by a trial ID only.

Data captured during phone calls to participants or from paper-based trial questionnaires returned to the trial office will be entered into the trial database by suitably trained central trial team staff. Full details of this process will be recorded in the Data Management Plan. Identifiable data will only be accessible by members of the research team with a demonstrated need (managed via access controls within the application) and only used to communicate with the participant (e.g. for sending follow-up reminders for online form completion or telephone follow-up).

